***For protocols that meet the criteria for exempt research, skip to Section 7.***

### **5 PARTICIPANT PAYMENT**

#### **5.1 Describe any compensation that will be given to participants for the completion of research-related activities. Include the monetary value and type of compensation per activity.**

**Aim 1 - Qualitative Review:** All participants will receive a \$30 Amazon gift card for participating in their 60-90 minute focus group, and may be contacted for a brief follow-up to answer clarification questions if needed.

**Aim 2 - Training Intervention:** In addition to the free training, all counselor participants will receive a \$50 Amazon gift card for each of the three (pre- and post-tutorial and 12-week follow-up) audio taped sessions (\$150 total). Participants in the TMC condition will have the opportunity to get certified in CRAFT at the end of the 12 week training, and participants in conditions T and TM will have the opportunity to do so after their participation in the study is complete.

#### **5.2 Describe any reimbursements that will be given to participants to repay them for costs they may have incurred over the course of the study. Include the monetary value and type of compensation per activity.**

N/A. We will not reimburse participants for any costs that they may incur for participating in this online study, including data or internet plans.

### **6 INFORMED CONSENT**

**6.1 Provide a brief summary of the informed consent process by selecting all of the consent procedures you will use and specifying for which study procedures. Complete the corresponding appendix as indicated.**

Consent Process	Specific Study Procedures
 Standard written informed consent	All Aim 1 and Aim 2 activities
 Waiver of documentation of consent (Appendix D)	
Alteration of informed consent ( Appendix D )	
 Waiver of informed consent ( Appendix D )	
 Short form ( Appendix E )	
Child assent and parental permission (Appendix I)	
 Waiver of child assent ( Appendix I )	
 Waiver of parental permission ( Appendix I )	

**6.2 Describe in detail the assent and/or consent procedures in chronological order. Include information about: how, when, where, and by whom (by position or role, not by name).**

**Aim 1 - Qualitative Review:**

All participants will be consented using the IRB-approved digital consent form prior to enrollment in the study. Upon completing screening and meeting eligibility requirements via phone or online survey, participants will have the option to complete the informed consent process immediately. They will be sent a link to the written digital consent form that will remain open for a period of 48 hours. The form will provide a description of the study and specify risks and discomforts, potential benefits, confidentiality measures, compensation, and the voluntary nature of their participation. A contact number will be provided for those who wish to ask questions before signing.

Because informed consent will be obtained using online methods, a written signature will not be possible. We will require participants to check a box agreeing to join the study and to type in their first and last name. We will download the checked consent form and save the file as a PDF in a protected folder secured on PHMC's network drive. All participants will receive an automatic email from Alchemer after completing the consent form. In addition, all participants will be able to download a copy of the informed consent form with the box agreeing to join the study checked off and with their name typed into the "I agree" section.

**Aim 2 - Training Intervention:**

Eligible participants will have the option to complete the informed consent process immediately after completing the Screening Survey if they meet eligibility requirements. They will be directed to click a link that will remain open for a period of 48 hours. They will be provided a brief explanation of time estimates for enrollment activity prior to clicking the appropriate link. After clicking the link, they will be directed to a self-administered online consent form. The form will provide a description of the study, specify risks and discomforts, potential benefits, confidentiality measures, compensation, and the voluntary nature of their participation. A contact number will be provided for those who wish to ask questions before signing.

Informed consent will be obtained using online methods, so a written signature is not possible. We will require participants to check a box agreeing to join the study and to type in their first and last name. We will download the checked consent form and save the file as a PDF in a protected folder secured on PHMC's network drive. All participants will receive an automatic email from Alchemer after completing the consent form. In addition, all participants will be able to download a copy of the informed consent form with the box agreeing to join the study checked off and with their name typed into the "I agree" section.

### 6.3 Describe any measures to ensure or test participants' understanding of the information presented during the informed consent process.

All participants will be provided with a telephone number for a research coordinator who will provide the opportunity to ask questions about the consent forms or to receive additional information about the study.

### 6.4 If a child who provided assent to participate in the study becomes 18 years old during the course of the study, describe the process to re-consent the participant.

N/A. We will not enroll children. Study participants must be over 19 years old (which meets or exceeds the criterion age of legal consent in all 50 states).

## 7 STUDY DATA

### 7.1 Select all of the personal identifiers you will access and obtain during this study.

*Access* means to view or to perceive data, but not to possess or record it. *Obtain* means to possess or record in any fashion (writing, electronic, video, email, voice recording, etc.) and to retain for any length of time.

 Names	 Account numbers
 Address (street address, city, county, precinct, ZIP code)	 Certificate/license numbers
 Dates related to an individual (birth date, admission/discharge dates, date of death)	 Vehicle identifiers and serial numbers
 Telephone numbers	 Device identifiers and serial numbers
 Fax numbers	 Web URLs
 Electronic mail addresses	 Internet protocol (IP) addresses
 Social security numbers	 Biometric identifiers including fingerprints and voiceprints
 Medical record numbers	 Full-face photographic images
 Health plan beneficiary numbers	 Any other unique identifying number, characteristic, or code

### 7.2 Does your study involve PHI and need to comply with HIPAA regulations?

HIPAA regulations apply to covered entities that access, collect, use, or disclose protected health information (PHI). PHMC is a HIPAA-covered entity and thus, **any study that involves PHI must comply with HIPAA regulations**. HIPAA only covers identifiable health information. Studies that involve only (A) health information without any of the 18 personal identifiers listed above or (b) non-health related information that contain identifiers do not need to comply with HIPAA because neither form of data meets the definition of PHI. Use the guide below to verify if your study involves PHI.

**All or some** study data:

(a) Contain one or more of the 18 personal identifiers.	 Yes  No	If you answered "No" to (a), then HIPAA regulations do NOT apply.
(b) Relate to an individual's past, present, or future physical or mental health or condition.	 Yes  No	If you answered "Yes" to (a) AND (b), (c), or (d), then HIPAA regulations apply to this project . Submit Appendix C .
(c) Relate to an individual's past, present, or future provision of healthcare.	 Yes  No	

(d) Relate to an individual's past, present, or future payment for the provision of healthcare.	 Yes  No	
---	---	--

### 7.3 Is there a possibility that *de-identified* information or biospecimens will be used for future research studies or distributed to another investigator for future research studies without additional informed consent from participants?

*This only applies to studies that prospectively collect information or biospecimens. Select "No" if your study involves secondary analysis only.*

Yes, de-identified information or biospecimens may be used or distributed for future research.  
 No, de-identified information or biospecimens will not be used or distributed for future research.

## 8 PRIVACY AND CONFIDENTIALITY

### 8.1 Describe procedures to protect participants' privacy during the study (i.e., precautions you have taken to protect the participant from being recognized as a research subject).

1. The participant enrollment spreadsheet will be password-protected and sent to WTV via encrypted email. (WTV will be responsible for contacting enrolled participants to inform them of their random assignment, to discuss next steps, if needed, and to provide a \$50.00 gift card incentive payment for completing a survey.)
2. Electronically obtained consent forms will be stored in a separate, restricted folder located on a secure network drive at Public Health Management Corporation, accessible only by key study staff.
3. When contacting participants for study-related purposes, staff will follow a locating and contact protocol that will decrease the chances of someone being identified as a research subject. They will leave messages approved by the participant that do not identify the person as a research participant.
4. Participants will be instructed to create a username that does not use their last name or email address. Participants can request for their usernames to be changed at any time during the study.
5. Participants will be instructed to make sure that they are in a private area before revealing any personal information while completing assessments and during an online focus group, interview, training, or, if applicable, during a video or telephone meeting with a CRAFT trainer or an audio taped session with a client. They will also be asked to consider using private telephones (no extension lines) when possible. For those participating via Zoom, Zoom ensures information is not stored in their network; the data is only transmitted during a session. WTV will pay to use a HIPAA protected Zoom account to reduce risks associated with privacy. Participants will receive a secure link to access sessions, so no one other than the intended counselor and staff can attend. Participants who elect to receive text messages or emails will be instructed to use a password to access telephone/email content and to delete messages immediately after responding to them. Focus group participants will be instructed to keep the identity of other participants in the group private.

### 8.2 Describe all of the procedures you will use to protect participants' confidentiality during the study (i.e., precautions you have taken to protect participants' data from being unnecessarily and inappropriately disclosed; e.g., authorization of access, password protection, encryption, physical controls, certificates of confidentiality, separation of identifiers and data). Include information on any measures that will be taken during storage, access, use, and transmission of study data.

*If you will obtain information on participants' substance use disorder from a treatment provider, then only answer this question for all other data not related to substance use records (e.g., self-report data). All confidentiality and data security questions around substance use records should be recorded in [Appendix J](#).*

1. Participants will be assigned an identification number which will be affixed to all collected assessment data. Linkage between participant identity and identification numbers will be stored in a password protected electronic file on a secure network drive at Public Health Management Corporation accessible by key study staff.
2. The password-protected participant enrollment sheet will not be connected to study data. Data collected in the study will be kept strictly confidential and will not be shared with anyone outside of the research team.
3. All computer spreadsheets containing data and SPSS data sets will be saved in password protected files on a secure server located at Public Health Management Corporation and accessible only to designated research staff.
4. All research instruments will be computerized for this study, and the data will be entered via the Web using SurveyGizmo platform. R&E Group maintains a Business Associate Agreement with Alchemer (formerly called Surveygizmo), allowing staff to securely collect private and confidential information in compliance with the Health Insurance Portability and Accountability Act (HIPAA), Family Educational Rights and Privacy Act (FERPA), and other applicable data security and protection laws.
5. All study staff will be required to undergo training in confidentiality procedures which reviews data handling procedures as well as addresses questions about participants posed by individuals outside of the immediate project staff and by project staff members who do not need the information requested. Certification of successful completion of this training is kept in the appropriate project folder. Should any breaches of participant confidentiality occur during the course of the study, they will be reported to the relevant IRB and DSMB.
6. Focus group participants will be instructed to keep the information shared by other participants in the group confidential.

**In addition, for Aim 2:**

7. Data collected as part of the online training activities will also be kept confidential. Participants will be instructed to create a unique username that does not use their last name or email address. For those participating in training activities via Zoom, Zoom ensures information is not stored in their network; the data is only transmitted during a session. We will provide participants with a secure link to ensure no one other than the participant can enter. WTV agreed to purchase the higher-level membership account that is HIPAA compliant.
8. Participants will be completing standard patient sessions for review and coding. Audio will be recorded by our trained SP and uploaded to a secure system similar to the one that [name] uses when providing counselor training, and then deleted from the recording device. Participants in the TMC condition (n=15) will also be submitting their own audiotaped sessions with actual clients for review, coding, and feedback by our CRAFT trainer. Once the counselor has uploaded the audiotape and it has been verified by the CRAFT trainer, it will be deleted from the recording device.
9. CRAFT trainers will code CRAFT procedure session fidelity using the coding checklist. Additional research team members will access the audiotapes and checklists for the purpose of developing an automated system to electronically code procedure fidelity in the same manner that CRAFT trainers. The checklists will not have a participant's name or other identifying information on them. They will only have their ID numbers.
10. After collecting and cleaning all data from the baseline and follow-up time points, PHMC will upload the final clean and de-identified data set to the study's secure Google drive in order to share the data with the study's statistician for analysis purposes.

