## 1.2 List the primary and secondary aims, research questions, and hypotheses.

**The goal of this project is to develop and evaluate the technical feasibility and commercial viability of a scalable digital counselor training program for CRAFT.** This Phase I project will develop an enhanced training model for CRAFT and digitize it to maximize scalability. In this project, we will:

**Aim 1:** Produce the digital counselor training prototype and coaching process, tailored to OUD - with stakeholder input.

**Aim 2:** Conduct a pilot study of 3 levels of digital training (Level 1 – Digital tutorial only [T]; Level 2 – Tutorial & digital training materials for self-study [TM]; Level 3 – Tutorial, digital materials, feedback and coaching [TMC]) to

establish feasibility, acceptability, and examine the effects of training on CRAFT knowledge, fidelity, and treatment entry and retention.

1. Primary Hypothesis
  - 1.1. At 12 weeks (after study start), participants assigned to the TMC condition will demonstrate the highest CRAFT procedure fidelity (measured in audiotaped sessions with a standardized patient) followed by TM and then T.

*Rationale:* Direct observation measuring content of CRAFT delivered in treatment sessions is our primary outcome as this provides the best assessment of counselor adherence and skill and is consistent with previous studies. Our hypothesis that TMC will produce greater use of CRAFT than T (or TM) is based on the results from previous trials comparing a workshop only to workshops plus feedback and coaching.
2. Secondary Hypotheses
  - 2.1. Participants assigned to the TMC condition will demonstrate the highest CRAFT knowledge followed by TM and then T, in their 12-week knowledge test.

*Rationale:* Results from previous controlled trials have shown no differences in counselor knowledge pre- to post-workshop, but increases have been seen when fact sheets and supervision are added after the workshop.
  - 2.2. Participants will rate the programs satisfactory, useful and usable with similarly positive scores (3 on a 5 point scale or above) at each follow-up assessment point.

*Rationale:* Research shows (and with our own CRAFT Family product) that all programs are rated similarly satisfactory and useful.

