### 1.3 List the primary and secondary outcomes.

The primary outcome variable is the participant's demonstration of procedure fidelity, measured in audiotaped sessions with a standardized patient.

Secondary outcome variables include participant's CRAFT knowledge; participant's satisfaction with the program (website content and delivery); participant's perceived implementation potential; participant's monetary valuation of the program; and participant's report of IPs entering treatment via CSO report.

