### **Treatment Conditions:**

**Digital Tutorial (T)** - All participants will continue to have access to tutorial materials throughout the study. Participants assigned to the T condition receive ONLY the tutorial. Afterwards they will be encouraged via weekly emails that are a component of the training program to continue using the resources in the online tutorial to revisit the CRAFT lessons on their own during the 10-week period between post-tutorial follow-up and the final follow-up assessment.

**Digital Tutorial, with training materials (TM)** - Participants assigned to the TM condition will complete the tutorial and then receive access to the additional training materials. They will not receive any feedback or video-calls for coaching. They will be encouraged via weekly emails to continue to learn CRAFT on their own during the 10-week post-tutorial period by using the new resources in the online tutorial and the digital training materials.

**Digital Tutorial, with training materials plus feedback and coaching (TMC)** - Systematic feedback and coaching during the 10-week post-tutorial to final assessment period (12 weeks post-baseline) will be provided to only to the 15 participants assigned to the TMC condition. Participants will be required to submit audio taped sessions with clients. They will be provided with consent-to-audiotape forms that they will need to have the client complete prior to

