Participants will receive individual written Personal Performance Feedback on all audio taped sessions that they submit. This feedback is generated by two CRAFT certified trainers (i.e., CRAFT Trainer or CRAFT Coder) who access the digitally audio taped sessions via a secure server. The trainer listens to the audiotape and records a session content checklist that indicates key procedures for each module. For each key component, the trainer indicates whether it was addressed in the session, rates the quality of implementation for that component (1=poor to 5=excellent), and writes comments praising specific behaviors or making suggestions for further improvement. This feedback is password protected and emailed to the counselor. TMC participants will participate in weekly 30-min video-call Coaching Sessions. In addition, the audio taped client sessions will be accessed by research team members charged with developing software that would automatically complete the coding currently done by the CRAFT trainers.

Table 2. Study Activities By Program

STUDY ACTIVITIES BY PROGRAM		
Tutorial	Tutorial + Materials	Tutorial, Materials, & Coaching
• Digital Tutorial providing CRAFT principles overview.	• Digital Tutorial providing CRAFT principles overview.	• Digital Tutorial providing CRAFT principles overview.

• Weekly emails encouraging continued use of the online tutorial to revisit CRAFT lessons.	• Additional training materials providing in-depth instruction on CRAFT protocol nuances and techniques.	• Additional training materials providing in-depth instruction on CRAFT protocol nuances and techniques.
	• Weekly emails encouraging continued use of the online tutorial and materials to revisit CRAFT lessons.	• Systematic feedback and coaching on CRAFT protocols and techniques 10-week period.
		• Program weekly emails encouraging continued use of the online tutorial and materials to revisit CRAFT lessons.

Figure 3. Recruitment and Enrollment Flowchart

**4.2 Briefly describe the sources or measures that will be used to collect data about participants. As applicable, include information on: instruments or surveys that will be administered, tests that will be performed, and the time points when each data will be accessed or obtained.**

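### The plan does not say who rates the primary-outcome tapes; the only fidelity-coding role it names also gives feedback in the TMC arm alone, with no masking stated

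*Protocol*

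**What the plan says.** Protocol section 1.3 defines the primary outcome as the counselor's "demonstration of procedure fidelity, measured in audiotaped sessions with a standardized patient". Section 4.2 places an SP session at each of the three assessments in every arm. It names a coding manual for those tapes but no rater.

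The passage closest to naming a rater is in section 8.2, under the Aim 2 additions. Item 8 opens with the SP sessions: "Participants will be completing standard patient sessions for review and coding". It then says that TMC counselors also submit client tapes "for review, coding, and feedback by our CRAFT trainer". Item 9 follows: "CRAFT trainers will code CRAFT procedure session fidelity using the coding checklist". On the checklists, item 9 adds: "They will only have their ID numbers".

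Section 4.1 says that feedback and coaching "will be provided to only to the 15 participants assigned to the TMC condition". It describes the source of the written feedback as follows: "This feedback is generated by two CRAFT certified trainers (i.e., CRAFT Trainer or CRAFT Coder".

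Section 1.2 states the expected direction, that "participants assigned to the TMC condition will demonstrate the highest CRAFT procedure fidelity", followed by TM and then T. The SAP's Data Analysis section tests improvement from baseline to week 12 with one-sided t-tests in that direction.

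**The concern.** Direct observation is a sound choice of primary outcome, but its value depends on raters who do not know which training a counselor received. The plan appears to give the rating to the role that also reviews and comments on TMC counselors' work over the 10 weeks before the final assessment. A TMC counselor may submit up to 12 client tapes in that time. A trainer who has heard several of them could recognise the voice on the week-12 SP tape, and so know the arm and have a view of the counselor's progress.

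Any leniency that followed would favour TMC, which is the direction of the one-sided tests. It would look like a training effect, and nothing in the planned analysis would reveal it.

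**Working it through.** **1. From outcome to rater.**
- The outcome is a rating of SP tapes (sections 1.3 and 4.2).
- SP tapes are to be coded (section 8.2, item 8), and CRAFT trainers code procedure fidelity (item 9). Item 9 does not name the SP tapes and could be read as covering client tapes only. On that reading the plan names no SP-tape rater at all. On either reading the rater's masking is unstated.
- CRAFT trainers give the feedback (section 4.1; section 8.2, item 8), and TMC alone receives it (section 4.1). The label CRAFT Coder does not separate the roles, because section 4.1 lists it as a source of the feedback too.

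**2. Safeguards in the readable text.**
- *ID-only checklists* (section 8.2, item 9). This is a confidentiality measure. It removes the name from the form but does not hide a familiar voice or the timepoint.
- *A coding manual* (section 4.2). This limits judgement. The client-tape checklist still includes a 1 to 5 quality rating (section 4.1); whether the SP-tape checklist does is not stated.
- *Change from baseline* (SAP, Data Analysis). Randomization follows the baseline tape (section 4.1), so familiarity arises after it. If tapes are coded as they arrive, leniency at week 12 does not cancel. If all are coded together later, part of it might. The plan does not say when coding is done.
- Nothing was found on masking to arm or timepoint, separation of raters from those giving feedback, tape order or double coding. Several figures could not be read.

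**3. Which comparisons are exposed.** Only TMC counselors receive feedback, so familiarity can separate TMC from the other arms but cannot tell TM from T. TMC v T is exposed. So is TMC v TM, where it counts as a planned comparison: the SAP's opening section lists only T with TM and T with TMC, while its Data Analysis section adds TMC v TM. TM v T is exposed only if coders know allocation, which the documents do not say.

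**4. Scale, for illustration.** There is no plan figure to reproduce: the documents give no alpha, SD or effect size for this outcome. Group sizes are those in the SAP (T 15, TM 16, TMC 16). Assume no true effect and a rating shift of b SD of the change score in favour of TMC. The pooled t statistic then follows a noncentral t distribution with

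df = n1 + n2 − 2, λ = b × √(n1·n2/(n1 + n2)),

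and the error rate is P(t > critical value).

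TMC v T: √(16 × 15/31) = 2.782, df 29. TMC v TM: √(16 × 16/32) = 2.828, df 30.

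| b (SD) | λ, TMC v T | TMC v T, 5% | TMC v T, 2.5% | TMC v TM, 5% |
|---|---|---|---|---|
| 0.1 | 0.278 | 8.5% | 4.5% | 8.6% |
| 0.2 | 0.556 | 13.5% | 7.8% | 13.7% |
| 0.3 | 0.835 | 20.3% | 12.5% | 20.7% |
| 0.5 | 1.391 | 38.7% | 26.9% | 39.6% |

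**5. Workload.** (15 + 16 + 16) × 3 assessments = 141 SP tapes at most.

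**The case against.** The case against has several parts.

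*Silence is not evidence of unmasked coding.* The key sentence sits in a confidentiality section, which asks about disclosure rather than bias, and the team may have masked its coders without saying so. This stands. A reader might infer that coding was unmasked; the documents do not say that, so any remedy for completed coding must wait for the facts.

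*A shared role title does not mean shared people.* A reader might infer that coaches rated their own trainees. The text does not support that. Item 9 does not name the SP tapes, item 8 ties the feedback trainer to client tapes, and section 4.1 refers to two trainers. What is shown is one role with both duties and no rule keeping them apart.

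*Not every comparison is affected.* A reader might infer that all three comparisons are compromised. For TM v T this would require coders to know allocation. Section 8.1 has the training company tell participants their assignment, but nothing says that coders see that list, and section 8.2 keeps the file linking identity to ID restricted.

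*The error rates rest on assumed bias.* This is correct. Any outcome shifted by an assumed amount gives such figures. They show sensitivity at this sample size, not an estimate for this trial.

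*It is a small pilot with few qualified trainers.* This bears on how much to ask. It argues against requiring new raters or compulsory double coding. It does not argue against relabelling tapes and shuffling their order, which existing staff can do.

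**Conclusion.** The concern holds in a limited form. In the readable text, the only role named to code procedure fidelity is also the role that gives feedback in TMC alone, and no safeguard masks raters or separates the two duties. Bias towards TMC is possible, not shown.

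The exposure is mainly in TMC v T, and in TMC v TM to the extent that it is a planned comparison. If ratings leaned towards TMC by 0.1 to 0.5 SD of the change score with no true effect, a one-sided 5% test of TMC v T would reject in about 8.5% to 38.7% of trials. That range assumes the alpha, the size of the shift and complete follow-up of 16 and 15 counselors. With masked ratings and no shift, the rate is the nominal 5%.

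This should be fixed: the safeguard is cheap and the outcome is the primary one.

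**What to change.** **If SP tapes remain to be coded:**
- State in the protocol who rates them.
- Give each tape a code that hides arm and timepoint and is not the study ID. Have the existing trainers or coders rate the tapes in random order, in one batch.
- Where two trainers are available, assign each TMC counselor's SP tapes to the one who neither reviewed that counselor's client tapes nor coached them. If this is not possible, keep the masked codes and random order, and report the overlap as a limitation of the TMC comparisons.
- Double-coding a subset to report agreement is useful but optional.

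**If coding is already done**, as the SAP's past tense suggests:
- First report who coded the SP tapes and what they knew of arm and timepoint.
- Only if coders were unmasked, or had given feedback to the counselors they rated, re-code the retained tapes in masked random order.
- If the tapes were not kept (section 8.3 gives no retention period for them), report this as a limitation of the TMC comparisons, and of TM v T as well if coders knew allocation.

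**Cost.** Relabelling and shuffling at most 141 tapes needs no new staff. The downsides are that coding is done later and that, where roles are separated, each TMC counselor's feedback must come from one trainer. Staffing is unclear (section 4.1 has two trainers, section 8.2 one), so separation may not be feasible; masked codes and random order do not depend on it. If re-coding proves necessary, it costs one further pass through the tapes.
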